#### **4.3.3.3 INR and Platelets**

The INR values and change from baseline will be summarized with descriptive statistics at baseline, Study Day 3, 7, 24 hours post last dose, 14 and 28. Baseline will be defined as the last non-missing INR value prior to first dose. Furthermore, change from baseline calculations will only include subjects with non-missing values at both baseline and the specific post-baseline visit will be included. A summary of platelets will also be presented similarly.

#### **4.3.3.4 Coagulation Panel, Organ Dysfunction and Exploratory Laboratory Results Analysis**

Coagulation Panel includes the following tests:

- Prothrombin time
- INR
- D-dimer
- Platelet count

Organ Dysfunction labs include the following tests:

- Serum creatinine
- Total Bilirubin
- PaO2/FiO2 ratio (only if vented)

Exploratory labs include the following tests:

- Coagulation: functional protein C, TAT, F1.2, PAI-1 and ATIII
- Inflammation: CRP, Microparticles and C5a
- Arterial lactate concentration

All efficacy laboratory evaluations will be presented in by-subject data listings.

Baseline is defined as the last non-missing value before first dose.

Summary statistics for actual values and for change from baseline will be tabulated for laboratory results by scheduled visit. Only subjects with baseline and non-missing post baseline values will be summarized at the specified time points. Figures of the mean (SD) and median (IQR) efficacy laboratory results (result and change from baseline) over time will be presented.

### **4.4 Analysis of Safety Endpoints**

#### **4.4.1 Clinical Adverse Events (AEs)**

Adverse events will be categorized and presented by primary system organ class (SOC), preferred term (PT), and grade of severity. The preferred term will be classified according to the Medical Dictionary for Regulatory Activities (MedDRA). The grade of severity will be estimated using the DAIDS Toxicity Table located in [Appendix I](#) of the protocol.

A treatment-emergent adverse event (TEAE) is defined as any AE following exposure to study treatment. For the purpose of calculating inclusion in summary tables, incomplete onset dates will be imputed as detailed in [Appendix A](#). All AE tables will include the total number of events, counting multiple events per subject and the number and percent of unique subjects with at least one occurrence of a preferred term according to the most severe DAIDS grade. A listing of subjects who have experienced AEs, along with their respective AEs, is also provided.

The AE reporting period for this trial begins after informed consent is signed and final eligibility criteria met and ends on day 28. Safety evaluation will be performed based on the actual treatment a subject has received.

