7.1.1 Severity of Adverse Events

The Investigator is to classify the severity of an AE using the DAIDS Toxicity Table provided in [Appendix I](#). If the toxicity table does not provide severity guidelines for certain events, the following definitions will be used:

Table 2: Guidelines for Grading AE Severity

Severity	Characteristic
Mild:	Symptoms causing no or minimal interference with usual social & functional activities
Moderate:	Symptoms causing greater than minimal interference with usual social & functional activities
Severe:	Symptoms causing inability to perform usual social & functional activities
Potentially Life-Threatening	Symptoms causing inability to perform basic self-care functions OR Medical or operative intervention indicated to prevent permanent impairment, persistent disability, or death

It is important to distinguish between serious and severe AEs. Severity is a measure of intensity whereas seriousness is defined by the criteria in **Section 7.2**. An AE of severe intensity need not

necessarily be considered serious. For example, nausea that persists for several hours may be considered severe nausea, but not an SAE. On the other hand, a stroke that results in only a limited degree of disability may be considered a mild stroke but would be an SAE.

If an adverse event changes in severity, the worst severity of the AE should be recorded. Should the AE become serious, the AE record will note an end date and a new entry for the SAE should be recorded with an onset date equal to the date the event met seriousness criteria.

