10.6.3 Adverse Events

The incidence of adverse events (AEs), treatment-related AEs, AEs leading to discontinuation, serious adverse events (SAEs), fatal adverse events and AEs by severity will be tabulated by treatment received. These AEs will be classified by system organ class and preferred term using the Medical Dictionary for Regulatory Activities (MedDRA). For incidence reporting, if a subject reported more than one AE that was coded to the same system organ class or preferred term, the subject will be counted only once for that specific system organ class or preferred term. Once the patient is authorized to randomize, SAEs will be collected through Day 28. Once randomization has occurred both AEs and SAEs are collected.

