#### **4.4.1.1 Incidence of Adverse Event**

An overall summary of TEAEs will be provided to summarize of the following information: unique subjects experiencing any AE, subjects with TEAEs, subjects with any serious TEAEs, subjects with any AE resulting in death or, leading to permanent discontinuation of study drug, and any study drug related TEAE as well as unique subjects with any AE by maximum severity grade. These summaries will be done by treatment group and overall. Furthermore, the above summary table will be repeated for any AEs overall which will include all TEAEs.

TEAEs will be summarized by the number and percent of subjects in each primary SOC and preferred term. Subjects will be counted only once for each primary SOC and each preferred term.

All AE data will be presented in a by-subject listing.

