#### **4.4.6 Bleeding Events**

A summary table for the number and percent of unique subjects with at least one major bleeding event during the 28 day study period, along with 95% exact confidence interval of the bleeding rate for each treatment and the exact risk difference between two treatment groups in bleeding rates, will be presented using the safety population. The count and percent of unique subjects experiencing at least one bleeding event by Study Days 3, 7, and 14 will be presented in the same table, but confidence intervals and risk difference will not be provided. Subjects will be counted as having experienced a major bleeding event from the earliest recorded event through all subsequent time points.

A bleeding event is considered on-treatment provided it occurs within five days past last dose. An after-treatment event is any event with an onset date of six or more days past last dose date. A summary of on-treatment and after-treatment major bleeding events will be presented by treatment arm and overall. If a subject experiences both an on-treatment and after-treatment event the subject will be counted in both summaries; that is, on-treatment and after-treatment event summaries may not be disjointed.

A similar summary will be presented for serious major bleeding events as well.

Additionally, the differences in major bleeding event rates will be presented by country, new infections, concomitant heparin use through day 7, renal function through day 7, baseline RRT, and on treatment RRT

Adverse events and serious adverse events identified as bleeding events will be summarized by primary system organ class (SOC) and preferred term (PT) for on treatment and off treatment separately.

All bleeding event data will be presented in a data listing.

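### An adverse event that turns serious is stored as two records with no rule to rejoin them, so descriptive event totals count it twice and a bleed near the window boundary can appear both on and off treatment

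*SAP*

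**What the plan says.** Three rules meet here.

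- **Recording (Protocol 7.1.1).** When an event turns serious, "the AE record will note an end date and a new entry for the SAE should be recorded with an onset date" set to the day seriousness was reached ("an onset date equal to the date the event met seriousness criteria"). A change in grade alone is treated differently: "If an adverse event changes in severity, the worst severity of the AE should be recorded". So a change in severity keeps one record, and a change in seriousness makes two.
- **Counting (SAP 4.4.1).** "All AE tables will include the total number of events, counting multiple events per subject". The same sentence also asks for unique subjects by preferred term. For subjects, SAP 4.4.1.1 adds "Subjects will be counted only once for each primary SOC and each preferred term", and Protocol 10.6.3 has the same rule.
- **Bleeding periods (SAP 4.4.6).** A bleed is on-treatment up to five days past the last dose. "An after-treatment event is any event with an onset date of six or more days past last dose date". Bleeding AEs and SAEs are then tabulated by SOC and PT, separately for on and off treatment.

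Protocol 7.1 records for every AE whether it involved bleeding, so a non-serious record can enter the bleeding tables. Neither document says how an AE and the SAE opened from it are to be treated in counts.

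**The concern.** The second record is the same clinical event at a later stage, but it has its own onset date and looks like a new event. A program that counts records will count one event as two. The total then partly reflects how many events were split, and not only how many occurred. The reset onset also matters wherever a table depends on onset date. In the bleeding tables, one continuous bleed can be shown once as an on-treatment AE and again as an off-treatment SAE.

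AEs and SAEs are primary safety endpoints, and SAP 3.7 plans no safety testing, so readers will rely on these descriptive tables. What is at stake is the accuracy of the event-total column and of one pair of bleeding tables. No inferential result is involved.

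**Working it through.** The documents state no event total that could be reproduced. The check traces the written rules through examples.

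**Step 1: records per event.** Protocol 7.1.1 gives one record for an event that never turns serious, or that is serious from the start. It gives two for an event that starts non-serious and turns serious. A table that covers all AEs therefore holds two entries for one event in one subject. An SAE-only table holds just the second record, so nothing is doubled there.

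**Step 2: effect on totals.** Let c be the share of distinct events that start non-serious and turn serious. Reported total = distinct events × (1 + c). The documents give no value for c. Purely as assumed values, c of 1%, 5%, 10% and 20% would turn 100 distinct events into 101, 105, 110 and 120. This is arithmetic on an assumption, not an estimate for this trial.

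**Step 3: bleeding periods.** For an uninterrupted six-dose course the last dose falls on Study Day 6. The on-treatment window ends on Day 6 + 5 = Day 11, and after-treatment starts on Day 6 + 6 = Day 12. Days past last dose = record onset − 6.

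| Bleed starts / turns serious (Study Day) | Days past last dose | Period of AE record | Period of SAE record |
|---|---|---|---|
| 3 / 5 | −3 / −1 | on | on |
| 9 / 11 | 3 / 5 | on | on |
| 10 / 12 | 4 / 6 | on | after |
| 11 / 12 | 5 / 6 | on | after |
| 4 / 13 | −2 / 7 | on | after |
| 8 / 15 | 2 / 9 | on | after |
| 12 / 14 | 6 / 8 | after | after |

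Every row yields two records for one bleed in one subject. Only rows whose dates lie on either side of the five/six-day boundary put that bleed in both periods. With fewer doses the boundary moves earlier by the same number of days.

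**Step 4: what stays intact.**

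- Subject counts: under the once-per-subject rule in SAP 4.4.1.1, a split pair with the same SOC and PT adds no subject.
- Severity: SAP 4.4.1.3 places each subject under the maximum grade.
- Major bleeding: Protocol 7.1 and Appendix B require every major bleed to be reported as an SAE, so the non-serious first record is not a major bleed. The 28-day summary counts unique subjects, and its confidence intervals rest on that count.
- Mortality: the primary analysis uses no AE records.

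**The case against.** The strongest reply is that the SAP never says an event is an eCRF record. On that view the gap is one of silence and the double count is inferred. This is fair as to wording. But Protocol 7.1.1 creates two dated entries, and SAP 4.4.1 asks for a total that counts multiple events per subject. Without a linking instruction, counting both is what the rules produce.

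A second reply is that SAP 4.4.6 already accepts overlap between periods and lists all bleeding data. Its overlap statement concerns a subject who has an event of each kind. It does not address one bleed held as two records. The listings would let a careful reader spot adjacent pairs, which limits the harm but does not correct the tables.

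A third reply is that the date seriousness was met is a reasonable onset for an SAE, and a reasonable date for a bleed that became major only then. This stands. Moving every serious or major bleed back to its first onset would be a different convention with its own bias, since it would call a bleed major during a period when it was not.

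A reader might go further in three ways that the documents do not support:

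- That major bleeding is counted twice. It is not, for the reason in Step 4 of the working.
- That the on/after split is meant to isolate bleeding caused by the drug, and so is defeated. SAP 4.4.6 states no purpose for the split.
- That the inflation can be sized, or is known to differ by arm. There is no conversion rate in the documents. The trial is double-blind and the recording rule is the same in both arms, so a difference in conversion could itself be a real safety difference.

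**Conclusion.** The point holds as a small correction to descriptive safety tables. Each AE that turns serious adds exactly one extra event to totals that include both records, and the aggregate effect cannot be stated from the documents. In the bleeding tables by SOC and PT, a single bleed can appear in both periods, but only when its start and its turn to serious lie on either side of the five/six-day boundary after the last dose.

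The conclusion assumes that events are counted from the records as Protocol 7.1.1 creates them, and that no linking rule exists outside the protocol and SAP.

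**What to change.** Add to SAP 4.4.1: *An AE and the SAE opened from it under Protocol 7.1.1 (same subject, same event, contiguous dates, confirmed by blinded review) are linked and counted as one event in event totals, at the worst severity and seriousness.*

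Add to SAP 4.4.6: *In the all-bleeding AE table by treatment period, a linked bleed is counted once, in the period of its first onset. The SAE and major-bleeding summaries keep the date seriousness was met. The first onset is listed beside it.*

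The link should not depend on an exact date match. Protocol 7.1.1 fixes the onset of the SAE record and says the AE record is given an end date, but it does not require the two dates to be equal. This is why the blinded review is needed.

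The cost is two SAP additions, a linking step in the AE dataset, and a blinded check of candidate pairs before unblinding. The endpoints, the subject-level tables and the primary analysis do not change.

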#### **4.4.1.1 Incidence of Adverse Event**

An overall summary of TEAEs will be provided to summarize of the following information: unique subjects experiencing any AE, subjects with TEAEs, subjects with any serious TEAEs, subjects with any AE resulting in death or, leading to permanent discontinuation of study drug, and any study drug related TEAE as well as unique subjects with any AE by maximum severity grade. These summaries will be done by treatment group and overall. Furthermore, the above summary table will be repeated for any AEs overall which will include all TEAEs.

TEAEs will be summarized by the number and percent of subjects in each primary SOC and preferred term. Subjects will be counted only once for each primary SOC and each preferred term.

All AE data will be presented in a by-subject listing.

#### **4.4.1.2 Relationship of Adverse Events to Study Drug**

A summary of TEAEs by relationship to study drug will be presented. A TEAE will be considered study drug-related if the investigator considered the event as possibly, probably or definitely related to treatment, or if the investigator assessment of the relationship is unknown. The TEAE data will be categorized and presented by primary SOC, preferred term, and relationship to study drug. Adverse events with missing relationship will be summarized as a related event and on the listings will be displayed as missing.

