As far as possible, each AE will also be described by:

- The duration (start and end dates)
- The severity grade (Grade 1/mild, Grade 2/moderate, Grade 3/severe, Grade 4/Potentially life threatening as defined by the DAIDS Toxicity Table)
- The relationship to the study drug (none, unlikely, related)
- Whether the AE involved bleeding of any kind
- The action(s) taken
- The outcome

Major Bleeding Events

A Major Bleeding event is defined as:

- any intracranial hemorrhage,
- any life-threatening bleeding,
- any bleeding event classified as serious by the Investigator (e.g., resulting in permanent morbidity),
- the administration of at least 1440 mL (typically 6 units) of packed red cells over two consecutive days.⁶

Note: Should a major bleeding event occur, study product must be discontinued.

All major bleeding events must be collected, documented, and promptly reported as SAEs.

Blood product administration will be recorded in the eCRF.

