7.1.2 Relationship of AE to Study Drug

The following table should be used as a guideline for assigning the relationship of the adverse event to the study drug.

Table 3: Guidelines for Grading Relationship of AE to Study Drug

Association	Definition
None (not related):	(1) The existence of a clear alternative explanation (e.g., mechanical bleeding at surgical site) or (2) non-plausibility, e.g., the subject is struck by an automobile or cancer developing a few days after drug administration.
Unlikely (remote):	A clinical event, including laboratory test abnormality (if applicable), with an improbable time sequence to drug administration and in which other drugs, chemicals, or underlying disease provide plausible explanations.
Related:	A clinical event, including laboratory test abnormality (if applicable), occurring in a reasonable time relationship to drug administration and which cannot be explained by concurrent disease or other drugs or chemicals. The response to withdrawal of the drug should be clinically plausible.

Adverse events judged as “Unlikely” or “Related” will be defined as “Adverse Drug Reaction”.

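### The SAP's rule for study drug-related TEAEs uses causality terms that are not on the protocol's none/unlikely/related scale, and neither document maps one to the other

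*SAP*

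**What the plan says.** Protocol 7.1 lists what is to be recorded for each adverse event, including "The relationship to the study drug (none, unlikely, related". Table 3 in Protocol 7.1.2 guides the choice among the same three levels. *Related* is for an event "occurring in a reasonable time relationship to drug administration and which cannot be explained by concurrent disease or other drugs or chemicals". *Unlikely* is for an event "with an improbable time sequence to drug administration and in which other drugs, chemicals, or underlying disease provide plausible explanations". Below the table the protocol adds a grouping: "Adverse events judged as “Unlikely” or “Related” will be defined as “Adverse Drug Reaction".

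SAP 4.4.1.2 uses other words: "A TEAE will be considered study drug-related if the investigator considered the event as possibly, probably or definitely related to treatment". The same sentence then widens the rule to events without a usable causality judgement: "or if the investigator assessment of the relationship is unknown". It goes on: "The TEAE data will be categorized and presented by primary SOC, preferred term, and relationship to study drug". For blanks it says: "Adverse events with missing relationship will be summarized as a related event and on the listings will be displayed as missing".

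The related/not-related distinction is then used in the overall TEAE summary and its repeat for all AEs (SAP 4.4.1.1) and in the related-SAE table (SAP 4.4.1.4). Protocol 10.6.3 also asks for the incidence of treatment-related AEs.

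**The concern.** A rule for classifying events has to be written in the categories that are collected. This one names three grades that, according to the protocol, investigators do not assign. The grades they do assign are not mentioned in it, so whoever programs the tables has to supply the mapping.

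Two questions are left open. The first is whether *Related* counts; it surely should, but the rule does not say so. The second is whether *Unlikely* counts. The SAP wording points to no, while the protocol puts *Unlikely* together with *Related* under one name.

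What is at stake is the content of a few descriptive safety tables, and that their definition is fixed before treatment codes are known. Under SAP 2.5 the sponsor is unblinded at the Day 28 database lock, so a mapping left open until then could be chosen with the results in view.

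**Working it through.** The plan gives no figure to reproduce. The check compares the two sets of categories and then follows each reading into the outputs.

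**Step 1. Inputs.**
- Protocol 7.1 and 7.1.2: {None, Unlikely, Related}.
- SAP 4.4.1.2, investigator judgement: {possibly, probably, definitely}.
- SAP 4.4.1.2, no usable judgement: {unknown, missing}, both counted as related.

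**Step 2. Overlap.** The protocol set and the SAP judgement set share no label: 0 of the 3 protocol levels appear in the SAP rule. Neither document contains a conversion, and SAP 4.4.1.2 mentions neither *Unlikely* nor the Adverse Drug Reaction grouping.

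**Step 3. Possible readings.**

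| Recorded state | (a) Labels matched exactly | (b) Natural reading | (c) Adverse Drug Reaction grouping |
|---|---|---|---|
| None | no | no | no |
| Unlikely | no | no | yes |
| Related | no | yes | yes |
| Unknown or missing | yes | yes | yes |

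**Step 4. How subject counts differ, per arm.**
- (b) minus (a) = subjects with at least one *Related* TEAE and no TEAE of unknown or missing relationship.
- (c) minus (b) = subjects with at least one *Unlikely* TEAE and no TEAE that is *Related*, unknown or missing.

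Neither difference can be given a number, because the documents contain no counts by causality level.

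**Step 5. Outputs that depend on the reading.**
- SAP 4.4.1.1: the related-TEAE line of the overall summary, and the same line when the table is repeated for all AEs.
- SAP 4.4.1.2: the by-relationship table. It is affected less, because it can be laid out on the recorded levels.
- SAP 4.4.1.4: the related-SAE table.
- Protocol 10.6.3: treatment-related AE incidence.

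**Step 6. Outputs that do not depend on it.** Efficacy, the all-cause AE and SAE summaries, and the major bleeding analysis in SAP 4.4.6 do not use causality. SAP 3.7 says safety endpoints are not tested, so no p-value turns on the definition.

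**The case against.** The strongest reply is that nobody would be misled. *Related* is the protocol's only positive grade, and any of the SAP's three terms describes an event related to treatment. A competent programmer would count *Related* and leave out *Unlikely*, so the defect is terminology that does not fit this protocol. All AE and SAE data are listed by subject, so the tables could be rebuilt on any definition. This largely stands, and it is why the point is minor. It does not remove the mismatch: a prespecified rule should not depend on the programmer choosing the intended mapping.

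Three stronger readings are tempting, and the documents do not support them.

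- A reader might infer that the related tables will contain only unknown or missing assessments. That follows only from matching labels word for word, and it is not the likely output.
- A reader might infer that the protocol requires *Unlikely* to count as study drug-related. It only names a grouping. No analysis section uses that term, and Protocol 10.6.3 asks for treatment-related AEs.
- A reader might argue that an event with plausible timing and a plausible alternative cause would be *possibly* related in the SAP's terms but has no place on the protocol scale. The SAP never defines *possibly*, and the protocol offers Table 3 as a guideline. Any gap between its rows belongs to the protocol scale, and rewording the SAP would not close it.

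**Conclusion.** The point holds as a minor inconsistency between the two documents. SAP 4.4.1.2 states its rule in categories that the protocol does not collect, does not name *Related*, and leaves the handling of *Unlikely* unstated. Only descriptive safety outputs are touched, and the number of subjects affected is not derivable.

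Confidence is high that the texts do not match. It is lower on how events would in fact be classified, because the eCRF is not among the documents. The conclusion assumes that the form uses the scale given in Protocol 7.1. If it records possibly, probably and definitely instead, the SAP rule would work, and the mismatch would lie between the protocol and the form.

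**What to change.** Before unblinding:

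1. Confirm the causality levels on the eCRF.
2. Restate SAP 4.4.1.2 on the protocol's levels. A TEAE is study drug-related if it is graded *Related* or if the relationship is unknown or missing. Say explicitly that *None* and *Unlikely* are not counted.
3. Show the by-relationship table on the levels as recorded.
4. Apply the same rule in SAP 4.4.1.1, including the repeat for all AEs, and in 4.4.1.4. Use it for the treatment-related AE incidence in Protocol 10.6.3.

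A supplementary column for *Unlikely* or *Related* combined would show the protocol's Adverse Drug Reaction grouping, but it is optional. The cost is a reworded SAP sentence with matching cross-references. No new data are needed.
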